A GuLF STUDY Scientific Advisory Board will be established as a subcommittee of the NIEHS Board of Scientific Counselors to provide additional oversight. This Board will include one or more members of the Board of Scientific Counselors, scientific experts, community representatives and Federal agency representatives. A separate Community Advisory Board, consisting of representatives of key study populations in the affected states, also will be established. Through funding made possible by a Gift to the NIH, the NIH has arranged to have the Institute of Medicine review the initial plans for the study and monitor study progress. The IOM held its first meeting focused on the GuLF STUDY on September 22, 2010. It is expected that the IOM will meet twice a year for several years, and then annually to review study progress and findings. An Interagency working group made up of representatives from each Federal Agency involved in some aspect of the oil spill response met on August 19, and is also expected to meet regularly to provide study oversight.

6 Statistical Analysis Methods

6.1 Treatment of Exposure Status and Health Outcomes

Estimates of quantitative levels for specific exposures will be developed to the extent possible by the industrial hygiene team. Exposure status (e.g. any contact with crude oil, dispersants, or relevant crude oil specific chemicals, e.g., benzene, heavy metals, etc.) will also be defined dichotomously as “exposed” or “unexposed” based on the definitions given above for the study population and an activity-based exposure reconstruction (Sections 3.1.1 and 3.1.3). Similarly, health outcomes will be examined quantitatively where appropriate (e.g., FEV1/FVC, CBC measures), and will also be defined as “present” or “not present” based on the existence of specific endpoints within each disease area of interest (respiratory, cardiovascular, hematologic, dermatologic, neurologic, cancer, reproductive, mental health, immunologic, renal, liver).

We expect that very few workers engaged in clean-up *related* tasks, but not in clean-up *per se*, such as those providing only administrative, logistical, or personnel support, will be enrolled in the cohort because of the initial screening. However, any such workers found to be enrolled in the cohort will be placed in an “unexposed worker” category and excluded from most analyses because their exposure profile will be fundamentally different from that of the other clean-up workers and they are likely to differ in important, potentially unmeasured, respects (e.g., physical activity, socioeconomic status, health care access or quality) from the other clean-up workers. We will revisit this approach after examining results from the mini-pilot to determine whether this should be incorporated into the full study.

6.2 Statistical Methods to Address Study Objectives

The objectives of this study are to evaluate and characterize relationships between exposures to oil, oil byproducts and/or chemical dispersants, and stress associated with the disaster and short- and long-term health effects. General analysis methods to address these objectives are as follows:

- **Descriptive analyses** will be conducted as a precursor to other investigations. Rates and proportions will be estimated and bivariate relationships will be explored using cross tabulations. 95% confidence intervals (CIs) will be estimated where appropriate.
- **Acute- and Short-term Outcomes:** Acute- and short-term health effects that may have been incurred during or immediately following exposure will primarily be assessed during baseline data collection and in the immediate follow-up time-period. Relationships between exposures and these outcomes will be investigated at the most basic level by fitting regression models: logistic regression models for dichotomous outcomes to estimate odds ratios (ORs) and 95% confidence intervals (CIs) for each exposure and least squares regression for continuous outcomes to estimate betas and standard errors (SEs) for each exposure. Relevant demographic variables (e.g., sex, age, race, socioeconomic status indicators) and other exposures will be included in the regression models as covariates and effect modifiers. More refined analyses will incorporate specific characterizations of exposure, such as type of work performed, location, nature, and duration of exposure, protective equipment used, and ultimately a quantitative index of exposures developed by a panel of industrial hygienists and other exposure experts to reflect the risk factors of interest.

Outcomes that will be evaluated include respiratory symptoms, nausea, headaches, dermatitis, depressive symptoms, anxiety, FEV1/FVC, CBC components, WBC differentials, DNA damage, etc.

- **Long-term Outcomes:** Long-term health effects that may be incurred in the years following the exposure will be assessed at regular intervals through follow-up by interview or linkage with disease/mortality registries. Relationships between exposures and dichotomous health outcomes will be investigated by fitting binomial repeated measures models to each outcome, using standard statistical software such as SAS Proc GENMOD and Proc MIXED. Exposure effects will be assessed via ORs for each observation period. Non-dichotomous outcome measures will be investigated using generalized linear models; appropriate transformations will be used to satisfy model assumptions. Relevant demographic variables (e.g., sex, age, race, SES indicators) and other exposures (including ongoing, repeated environmental variables where available) will be included in the repeated measures models as covariates. These outcomes will include cancer, neurological (neurocognitive, neurobehavioral, neurophysiological) deficits, cardiovascular injury, reproductive effects, persistence of early effects, among others.

Various refinements to these basic methods as well as these additional analyses will also be pursued:

- **Confounding and Effect Modification:** Potential confounders and effect modifiers will be introduced into the models to determine the extent to which they might influence any effect. A potential confounder will be retained in the model if its inclusion changes the estimated effect of an exposure or the length of its 95% confidence interval by 10% or more. Stratified analyses will also be used, as appropriate. Information on many of these factors will be obtained by interview, but others may come from analysis of biologic specimens. In addition, we will perform sensitivity analyses to assess the impact of unmeasured confounders, classification errors (for both exposures and outcomes), and selection bias on estimates of exposure-disease association. This will be done in part using probabilistic methods to quantify the likely effects of misclassification of dichotomous measures [Fox, et al. 2005, Chu, et al. 2006] and polytomous measures [Arah, et al. 2008].
- **Repeated measures:** Repeated measurements on individual components of long-term health outcomes (examples: reported numbers of days experiencing asthma symptoms, FEV1/FVC) will be investigated for association with exposure through repeated measures mixed-effect models, while introducing appropriate effect modifiers. In particular, pulmonary function measures provide objective data that complement less objective self-reported symptom data, but are typically quite variable. Results from other studies suggest that, at a given time point, we can expect to detect differences in FEV1 as low as 5% between subgroups of about 250 participants per group with 80% power. Analyses to compare larger subgroups, compare groups across multiple time points, detect changes over time, or investigate the FEV1/FVC ratio all involve more stable measures or comparisons and so will exhibit greater statistical power.

- Non-reversing binary prospective outcomes, such as incident diagnoses, will also be modeled using Cox proportional hazards models.

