Table 3 presents minimum detectable odds ratios across a range of proportions of exposure among the workers and of health outcome among the controls. Estimates are shown separately for analyses of the full cohort and of the Active Follow-up Sub-cohort, including all controls or including only the non-local controls. Estimates are also shown for analyses of the Biomedical Surveillance Sub-cohort. All estimates are based on a two-sided test with $\alpha=5\%$ and power=80%. As the table shows, this study has excellent power to detect small risks, except when exposure or outcome is rare. For example, in an analysis of the full cohort, if 10% of the workers received a given exposure (e.g., high exposure to VOCs) and the incidence or prevalence of disease is 1%, this study would have sufficient power to detect an OR of at least 1.56 when using all 12,000 controls and 1.86 when using only the 2,500 non-local controls. In an analysis restricted to the Active Follow-up Sub-cohort, with proportion of exposure of 10% and disease incidence/prevalence of 10%, the minimum detectable OR would be only 1.30 when using the full control group (N=5,000) and 1.38 for the non-local control group (N=1,500). The Biomedical Surveillance Sub-cohort, with 4,500 workers and 500 controls, provides adequate statistical power to detect odds ratios of at least 1.59 when 25% of workers received a given exposure and the incidence or prevalence of disease is 10%. For perspective, estimated relative risks of lower respiratory tract symptoms observed among clean-up workers in previous oil spills ranged from 1.5 to 3.6 [Janjua, et al. 2006, Zock, et al. 2007, Meo, et al. 2009, Sim, et al. 2010]. Thus GuLF STUDY is sufficiently powered to observe such prevalence or relative risks for these outcomes.

Table 3. Minimum detectable odds ratios for a range of proportions of exposure among the workers and for all controls vs. non-local controls, based on a two-sided test with $\alpha=5\%$ and power=80%

Size of control group (i.e., all vs. non-local)	Proportion (N) of workers exposed to a given agent					
	5%	10%	25%	50%	75%	100%
Full cohort: 43,000 workers, 12,000 controls:						
	N=2,150	N=4,300	N=10,750	N=21,500	N=32,250	N=43,000
Proportion of controls with outcome=1%						
12,000 ^a	1.74	1.56	1.41	1.35	1.33	1.32
2,500 ^b	2.02	1.86	1.76	1.72	1.71	1.70

Proportion of controls with outcome=10%

12,000 ^a	1.23	1.17	1.13	1.11	1.10	1.10

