2,500 ^b	1.30	1.25	1.22	1.21	1.21	1.21

Proportion of controls with outcome=30%

12,000 ^a	1.15	1.11	1.08	1.07	1.07	1.07
2,500 ^b	1.19	1.16	1.14	1.14	1.14	1.13

Active Follow-up Sub-cohort: 15,000 workers, 5,000 controls:

	N=750	N=1,500	N=3,750	N=7,500	N=11,250	N=15,000
--	--------------	----------------	----------------	----------------	-----------------	-----------------

Proportion of controls with outcome=1%

5,000 ^a	2.33	1.98	1.71	1.59	1.55	1.53
1,500 ^b	2.66	2.34	2.11	2.02	1.99	1.97

Proportion of controls with outcome=10%

5,000 ^a	1.40	1.30	1.21	1.18	1.17	1.16
1,500 ^b	1.47	1.38	1.31	1.29	1.28	1.28

Proportion of controls with outcome=30%

5,000 ^a	1.26	1.19	1.14	1.12	1.11	1.11
1,500 ^b	1.31	1.25	1.20	1.19	1.18	1.18

Biomedical Surveillance Sub-cohort: 4,500 workers, 500 controls:

	N=225	N=450	N=1,125	N=2,250	N=3,375	N=4,500
--	--------------	--------------	----------------	----------------	----------------	----------------

Proportion of controls with outcome=1%

500 ^a	4.62	3.86	3.32	3.11	3.04	3.00
------------------	------	------	------	------	------	------

Proportion of controls with outcome=10%

500 ^a	1.92	1.73	1.59	1.54	1.53	1.52
------------------	------	------	------	------	------	------

Proportion of controls with outcome=30%

500 ^a	1.60	1.47	1.38	1.35	1.33	1.33
------------------	------	------	------	------	------	------

^a All controls in cohort/sub-cohort

^b Non-local controls in cohort/sub-cohort

Minimum detectable differences for continuous outcomes are presented in Table 4. Differences are expressed in standard deviations (SDs) and are based on a two-sided test with $\alpha=5\%$ and power=80%. Results are shown separately for analyses of the full cohort and of the Active Follow-up Sub-cohort including all controls or including only the non-local controls. In addition, estimates are shown for analyses of the Biomedical Surveillance Sub-cohort. This table demonstrates that the present study has sufficient

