We will next conduct cross-sectional analyses, consisting primarily of comparisons of prevalence or extent of a given outcome by clean-up task or estimated exposure to a given factor (from the JEM). These will be performed using least squares regression for continuous outcomes or logistic regression for dichotomous outcomes, adjusted for confounders as appropriate. We will explore possible modifiers of effect such as race,

sex, baseline health characteristics, lifestyle factors, and access to health care by also conducting stratified analyses by these factors, as appropriate and as numbers permit.

When follow-up data become available, we will also be able to perform prospective analyses linking clean-up activities/exposures to incident outcomes using Cox proportional hazards regression. We will use logistic regression for nested case-control analyses. Extent of change of outcomes will be assessed using least squares regression. Confounding and effect modification will be addressed as described above.

Clinical protocols for a number of outcomes, including respiratory and neurologic effects, will be developed and carried out in collaboration with local university partners identified through a request for proposals (RFP). Therefore, analysis of these outcomes will be addressed in a later protocol.

8 Training, Quality Control, and Quality Assurance

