Both active and passive exposure to tobacco smoke are strongly associated with increased levels of metals and VOCs in blood. Approximately 38% of GuLF STUDY participants who have agreed to a Home Visit are current smokers (active smokers). Non-active smokers will be over-sampled in order to examine the potential contributions of non-tobacco sources to personal exposures. Although we now collect information on passive smoking during the telephone interview, until late February 2012, this information was collected only from those completing a home visit. Table 1, therefore, shows information on active and passive smoking for individuals who completed the home visit as of May 15, 2012. Approximately 35% of GuLF STUDY participants who are not active smokers report they are currently exposed to tobacco smoke in their home.

When selecting participants for the EM Addendum, we will apply sampling weights so that at least 80% of the participants are not active smokers. Thus based on current rates of passive exposure, we expect that 20 percent will be active smokers and 28% will be passive smokers ($0.8 \times .35$) for a total of 48% with smoke exposure and 52% unexposed.

Table 1. Active and Passive Smoking Status among GuLF STUDY participants
Passive Smokers

		Currently Exposed to Tobacco Smoke in the Home				Total		
		Yes		No				
Active Smokers		N	%	N	%	N	%	
	Currently	Yes	966	63.8%	549	36.2%	1515	100%
	Smoke	No	858	34.9%	1600	65.1%	2458	100%

Currently about 20% of those eligible for a home visit are women. We will also apply sampling weights in order to target a sample that is at least 30% women.

A. Selection of Participants for EM Addendum (Phase I)

Beginning with participants who agree or tentatively agree to a home visit (about 83% of GuLF STUDY participants), we will invite 1,200 (300 per state) to provide the additional samples for the EM Addendum to achieve a final sample size of approximately 1,000 participants with complete data and samples (83% participation). This accounts for the loss of participants between agreement and final completion (currently 15%) and allows for some additional losses due to inability to obtain the extra blood samples or secondary refusals.

B. Selection of Participants for Personal Environmental Monitoring (Phase II)

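### Read on the odds-ratio scale, the 10% rule for keeping confounders tolerates as much bias as the smallest effects the full cohort is said to detect, and the protocol does not state the scale

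*Protocol*

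**What the plan says.** Section 6.2, under Confounding and Effect Modification, retains a potential confounder "if its inclusion changes the estimated effect of an exposure or the length of its 95% confidence interval by 10% or more". The denominator and scale of that percentage are not given. The same section reports dichotomous effects as ORs and continuous effects as betas. It also says that relevant demographic variables (sex, age, race and socioeconomic indicators are the examples) and other exposures will be included as covariates. Smoking is not named there.

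Section 7.1 carries the rule into the prospective analyses: "Confounding and effect modification will be addressed as described above". Section 6.2 plans sensitivity analyses for unmeasured confounders, misclassification and selection bias. It plans none for measured confounders that the rule leaves out.

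Section 6.5.2 states: "As the table shows, this study has excellent power to detect small risks, except when exposure or outcome is rare". Its Table 3 lists minimum detectable ORs for two-sided 5% tests at 80% power. For the full cohort (43,000 workers) against all 12,000 controls, with 5%, 10%, 25%, 50%, 75% and 100% of workers exposed, the entries are "1.23 1.17 1.13 1.11 1.10 1.10" at a 10% outcome and "1.15 1.11 1.08 1.07 1.07 1.07" at a 30% outcome.

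The only smoking prevalence is in Addendum 1, section IV: "Approximately 38% of GuLF STUDY participants who have agreed to a Home Visit are current smokers". It is not split by worker and control.

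**The concern.** A change-in-estimate cut-off is harmless when the effects of interest are much larger than the cut-off. Here they are not. A covariate that explains the whole of an OR of 1.10 moves it to 1.00, a change of 0.10/1.10 = 9.1%, and so falls below the threshold. The CI-length criterion gives little protection, because on the OR scale the interval shortens as the OR falls.

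At stake are small positive ORs for common outcomes such as respiratory symptoms in the full cohort. If they can come from a measured factor that the rule allowed to be left out, they cannot be attributed to oil or dispersants.

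**Working it through.** **1. The plan's own figures.** I solved the pooled-variance two-proportion power formula for 80% power, two-sided 5%, 12,000 controls:

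- 10% outcome: 1.231, 1.173, 1.129, 1.110, 1.103, 1.100
- 30% outcome: 1.151, 1.113, 1.084, 1.072, 1.067, 1.065

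Table 3 reproduces to rounding (differences of at most 0.006).

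**2. Inputs for the illustration.** From the documents: group sizes and outcome frequencies (Table 3) and the 38% smoking figure. Assumed: that 38% applies to workers, smoking prevalence in controls (28%, 33%, 36%), a smoking-outcome OR of 2, a true exposure OR of 1, and all workers counted as exposed.

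**3. One case in full: full cohort, 10% outcome, 38% v 28% smokers.**

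- Outcome risk in non-smokers r0 solves 0.72·r0 + 0.28·2r0/(1+r0) = 0.10, giving r0 = 0.0808. In smokers r1 = 0.1495.
- Risk in workers: 0.62 × 0.0808 + 0.38 × 0.1495 = 0.1069.
- Crude OR: (0.10687/0.89313)/(0.10/0.90) = 1.077. The smoking-adjusted OR is 1.00.
- Change in OR: 0.077/1.077 = 7.1% of the crude value (7.7% of the adjusted value).
- Crude SE of log OR: √[1/(43,000 × 0.10687 × 0.89313) + 1/(12,000 × 0.10 × 0.90)] = 0.0342. With smoking in the model: 0.0345.
- CI length on the OR scale: 0.1445 crude, 0.1355 adjusted, a change of 6.2%.
- Both changes are below 10%, so the rule does not retain smoking. z = ln(1.077)/0.0342 = 2.17, and P(significant) = Φ(2.17 − 1.96) = 58%.

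**4. The same calculation across cases** (two-sided false-positive rate with smoking left out; nominal 5%):

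| Population | Smokers, workers v controls | 1% outcome | 10% outcome | 30% outcome |
|---|---|---|---|---|
| Full cohort, 43,000 v 12,000 | 38% v 28% | 11% | 58% | 89% |
| Full cohort | 38% v 33% | 7% | 19% | 35% |
| Full cohort | 38% v 36% | 5% | 7% | 10% |
| Active Follow-up, 15,000 v 5,000 | 38% v 28% | 8% | 28% | 52% |
| Biomedical Surveillance, 4,500 v 500 | 38% v 28% | 5% | 8% | 11% |

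In every row the OR and the CI length change by less than 10%. Including smoking restores the expected OR to 1.00 and the error rate to 5%. In the full cohort at 38% v 28% this widens the SE by 1.0% (10% outcome) and 1.6% (30% outcome).

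**5. Smaller cohort.** Addendum 3 reports nearly 33,000 people surveyed. With the same split, z falls by √(55/33) = 1.291. The 38% v 28% case then gives z = 2.167/1.291 = 1.68 (39%) at a 10% outcome and 3.178/1.291 = 2.46 (69%) at a 30% outcome.

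**6. What the rule permits at its limit.** An omitted bias just under 10% (OR 1.0999) with a true OR of 1 is significant in the harmful direction 80% (10% outcome) and 99% (30% outcome) of the time in the full cohort, and 42% and 77% in the Active Follow-up Sub-cohort.

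**7. The other scale.** On the log-OR scale the case in step 3 goes from 0.074 to 0, a change of about 100%, so smoking is retained and the bias does not occur.

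**The case against.** **The rule does not govern everything.** A reader might infer that any covariate moving the OR by less than 10% is discarded. The text does not support that. Demographics and other exposures are to be included anyway. Sections 2.1.3 and 2.9.3 say that prior oil, boat and remediation work and residential exposures will be addressed in the analyses. A factor is left out only if both criteria fall short. The wording is also a condition for retention, not an explicit order to drop. These points stand and narrow the issue to factors outside the stated covariates. Tobacco smoke could be argued to count as another exposure, but section 6.2 does not say so.

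**The scale is open.** The inflation needs the OR reading. A reader might infer that the rule fails on the log-OR scale too, because it keeps harmless covariates there. In simulations a pure non-confounder was kept in roughly half of the runs or more. That costs a little precision and creates no bias, so it is not a matching failure. Continuous outcomes, reported as betas, are not affected.

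**The scope is limited.** ORs of 1.07 to 1.10 occur only in the full cohort with all controls: at a 30% outcome with at least 25% of workers exposed, and at a 10% outcome with at least 75%. Explaining away an OR of 1.13 is an 11.5% change and would be caught.

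**The smoking gap is assumed.** The 38% covers everyone who agreed to a home visit. Controls come from the same training lists for comparability (section 2.2.1), so the gap may be small, and at 38% v 36% the inflation is slight. This stands as a limit on size.

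**An exact adjustment set may be left to an analysis plan.** That is so, but the 10% rule is itself written into the protocol, and the point concerns that rule.

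**Conclusion.** The concern holds in this limited form: on the OR scale, the 10% tolerance equals or exceeds the smallest effects claimed for full-cohort analyses of common outcomes and common exposures. A measured confounder not listed among the covariates, most clearly smoking, could be left out and alone yield a significant OR.

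The size depends on an assumed smoking gap. With a smoking OR of 2, a ten-point gap gives 58% to 89% false positives in the full cohort and a two-point gap gives 7% to 10%. The problem is moderate in the Active Follow-up Sub-cohort (28% to 52% at the ten-point gap). It is minor (about 11% or less) for a 1% outcome or in the Biomedical Surveillance Sub-cohort, and absent on the log-OR or beta scale.

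Because the scale is not stated, two analysts could both follow section 6.2 and reach different conclusions from the same data. The documents do not show that smoking will in fact be left out, or that workers and controls differ in smoking. They show a rule that would not prevent the bias if they do.

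**What to change.** In section 6.2, name a minimum adjustment set that stays in every model whatever the change in estimate: age, sex, race, socioeconomic indicators and current smoking. Add prior petrochemical, boat or hazard-remediation work, residence and passive smoke wherever these were collected for the population analysed. Confine any change-in-estimate rule to further covariates, and state its scale.

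The qualification on availability matters. Section 2.9.3 places the detailed occupational, residential and tobacco histories in the home-visit questionnaire. Addendum 1 says passive smoke was asked only at home visits until late February 2012. Addendum 3 gives about 11,200 home visits among nearly 33,000 people surveyed. The longer list therefore cannot be required for the whole cohort. Addendum 1 reports current smoking for people who had only agreed to a visit, which suggests that it comes from the telephone interview. The sponsor should confirm this.

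The cost is a wording change and standard errors about 1 to 2% wider.
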